18. The tumor assessment visit time window is ~~5 days prior to dosing (- 5 days) for tumor evaluation~~ **5 days prior to the planned tumor assessment date (- 5 days) according to first dosing day** during the Treatment Phase, and  $\pm$  5 days after the EOT Visit. CT or MRI scan (if MRI is used, CT of chest is mandatory) should always be used. CT/MRI scan will be performed at baseline, every 6 weeks (- 5 days) during the first 12 months of the study, and then every 12 weeks (- 5 days) until progression.

CCI

20. Disease response determinations, including progressive disease assessments associated with study endpoints, will be supported by tumor assessments performed by Investigator.

21. Premedication is mandatory approximately 30 to 60 minutes prior to the first 4 doses of avelumab. Premedication should be administered for subsequent avelumab doses based upon clinical judgment and presence/severity of prior infusion reactions. This regimen may be modified based on local treatment standards and guidelines as appropriate. However, the prophylactic use of systemic corticosteroids is not permitted.
22. Concomitant medications and procedures will be documented at each study visit ~~until the EOT Visit~~ **until the 30-day Safety Follow-up Visit**.
23. All AEs will be documented at each study visit until the 30-day Safety Follow-up Visit. After this visit, only treatment-related nonserious AEs have to be documented until the 90-day Safety Follow-up Phone Call.
24. All SAEs will be documented at each study visit until the 90-day Safety Follow-up Phone Call. After this, all ongoing SAEs must be monitored and followed by the Investigator until stabilization or until the outcome is known, unless the subject is documented as lost to follow-up. Any SAE assessed as related to study drug must be reported whenever it occurs, irrespective of the time elapsed since the last administration of avelumab. At 90 days ( ± 5 days) after the last dose of avelumab, subjects will be contacted by telephone to collect information on new or ongoing SAEs and treatment-related nonserious AEs.
25. Blood samples for PK and ADA will be collected as detailed in Table 1-3.
26. Subjects will be followed every 12 weeks ( ± 7 days) for survival (including assessment of any further anticancer therapy).

**Table 12-3 Schedule of Assessments for Subjects Receiving Avelumab Once a Week for the First 12 Weeks Followed by Once Every 2 Weeks (10 mg/kg Once Weekly Cohort)**

Assessment 	Clinical Screening / Baseline Assessments	Treatment Phase 													Until progression
	≤ Day -14 to Day -1	V1	V2	V3	V4	V5	V6	V7	V8	V9	V10	V11	V12	V13	
		W1	W2	W3	W4	W5	W6	W7	W8	W9	W10	W11	W12	W13 (Roll-over into Once every-2-weeks dosing)	
		D1	D8	D15	D22	D29	D36	D43	D50	D57	D64	D71	D78	D85	

CCI

Assessment 	Clinical Screening / Baseline Assessments	Treatment Phase 													Until progression
	≤ Day -14 to Day -1	V1	V2	V3	V4	V5	V6	V7	V8	V9	V10	V11	V12	V13	
		W1	W2	W3	W4	W5	W6	W7	W8	W9	W10	W11	W12	W13 (Roll-over into Once every-2- weeks dosing)	
		D1	D8	D15	D22	D29	D36	D43	D50	D57	D64	D71	D78	D85	
Written informed consent	X														
Inclusion/exclusion criteria	X														
Medical history 	X														
Demographic data	X														
Hepatitis B, hepatitis C and HIV tests	X														
Full physical examination 	X														
Symptom-directed physical exam 		As indicated throughout the Treatment Phase													
Height	X														
Vital signs	X	X	X	X	X	X	X	X	X	X	X	X	X	X	2-weekly
Weight	X	X	X	X	X	X	X	X	X	X	X	X	X	X	2-weekly
ECOG PS 	X	X 	X	X	X	X	X	X	X	X	X	X	X	X	2-weekly
Enrolment (if eligible) 	X														
12-lead ECG	X	X	X	X	As indicated and decided by Investigator										

Assessment 	Clinical Screening / Baseline Assessments	Treatment Phase 													Until progression
	≤ Day -14 to Day -1	V1	V2	V3	V4	V5	V6	V7	V8	V9	V10	V11	V12	V13	
		W1	W2	W3	W4	W5	W6	W7	W8	W9	W10	W11	W12	W13 (Roll-over into Once every-2-weeks dosing)	
		D1	D8	D15	D22	D29	D36	D43	D50	D57	D64	D71	D78	D85	
Hematology and hemostaseology	X		X	X	X	X	X	X	X	X	X	X	X	X	
Core serum chemistry 			X	X	X	X	X		X	X	X	X	X		2-weekly
Full serum chemistry 	X							X						X	6-weekly
Full urinalysis 	X														
Basic urinalysis 								X						X	6-weekly
Serum beta-hCG pregnancy test (if applicable) 	X														
Urine pregnancy test (if applicable) 		X				X				X				X	4-weekly
CCI															
Premedication 		X	X	X	X										

Assessment 	Clinical Screening / Baseline Assessments	Treatment Phase 													Until progression
	≤ Day -14 to Day -1	V1	V2	V3	V4	V5	V6	V7	V8	V9	V10	V11	V12	V13	
		W1	W2	W3	W4	W5	W6	W7	W8	W9	W10	W11	W12	W13 (Roll-over into Once every-2-weeks dosing)	2-weekly
		D1	D8	D15	D22	D29	D36	D43	D50	D57	D64	D71	D78	D85	
Avelumab administration		X	X	X	X	X	X	X	X	X	X	X	X	X	
Concomitant medication and procedures	Collected at each study visit until the EOT Visit until the 30-day Safety Follow-up Visit														
AE collection 	AEs are collected through the 30-day Safety Follow-up Visit Treatment-related nonserious AEs are collected until the 90-day Safety Follow-up Phone Call														
SAE collection 	All SAEs are documented until the 90-day Safety Follow-up Phone Call Ongoing SAEs at the 30-day Safety Follow-up Visit will be followed up														
Free T4 and TSH	X							X						X	6-weekly
PK sampling 	See Table 1-4														
ADA sampling 	See Table 1-4														
Survival 		X	X	X	X	X	X	X	X	X	X	X	X	X	Every visit
Further anticancer therapy 	Collected through Safety Follow-up and Long-term Follow-up														

ADA: antidrug antibody; AE: adverse event; CR: complete response; CT: computed tomography; D: Day; DLT: dose-limiting toxicity; ECG: electrocardiogram; ECOG PS: Eastern Cooperative Oncology Group performance status; EOT: End-of-Treatment; hCG: human chorionic gonadotropin; HIV: Human immunodeficiency virus; ICF: Informed consent form; IMP: investigational medicinal product; MRI: magnetic resonance imaging; PD: progressive disease; CCI [REDACTED]; PK: pharmacokinetics; PR: partial response; RECIST: response evaluation criteria in solid tumors; SAE: serious adverse event; T4: thyroxine; TSH: thyroid-stimulating hormone; V: Visit; W: Week.

1. A time window of 1 day before or 1 day after the scheduled visit day (- 1/+ 1 days) is permitted for all study procedures while subjects receiving avelumab once weekly (12 consecutive weeks). A time window of up to 3 days before or 1 day after the scheduled visit day (- 3/+ 1 days) is permitted for all study procedures while subjects receiving avelumab once every 2 weeks (Week 13 and thereafter). The calculation of the dose of avelumab will be based on the weight of subject determined within 72 hours prior to the day of drug administration.
2. **Columns of EOT Visit, Safety Follow-up, and the Long-term Follow-up Visits are omitted due to layout readability. The procedures at EOT Visit, Safety Follow-up, and the Long-term Follow-up are identical to the procedures planned for subjects receiving avelumab once every 2 weeks (as shown in Table 1-1).**
3. ~~2-~~ Mandatory for study entry. A recently obtained formalin-fixed, paraffin-embedded block containing tumor tissue (biopsy from a non-irradiated area within 6 months) or 12 or more slides (preferably, approximately 25 slides) is required for all subjects. Endoscopic biopsies, core needle biopsies, excisional biopsies, punch biopsies, and surgical specimens are suitable. Fine needle aspiration biopsies are not suitable. Samples can be provided as block or slides.
4. ~~3-~~ Medical history should include history of cancer, previous and ongoing medications, previous surgeries, radiotherapies, baseline medical conditions, smoking and alcohol history, and family cancer history.
5. ~~4-~~ A full physical examination will be conducted at Clinical Screening, at the EOT Visit and at the 30-day Safety Follow-up Visit. During the Treatment Phase, the physical examination will be symptom-directed.
6. ~~5-~~ If the Clinical Screening ECOG PS was performed within 3 days prior to Day 1, it does not have to be repeated at Visit 1/Cycle 1 Day 1.
7. ~~6-~~ Enrolment will be done after confirmation that the subject meets all screening inclusion criteria (Section 5.3.1) without matching any exclusion criterion (Section 5.3.2).
8. ~~7-~~ Core serum chemistry includes liver function panel (alkaline phosphatase, aspartate aminotransferase, alanine aminotransferase, bilirubin), acute chemistry panel (sodium, potassium, chloride, blood urea nitrogen/total urea, creatinine, glucose), and mineral panel (magnesium, phosphorus, calcium). If full and core chemistry are scheduled at the same visit, the full chemistry will be performed.
9. ~~8-~~ Full chemistry panel and other laboratory studies are detailed in Section 7.4.3. Follicle-stimulating hormone at Clinical Screening, if applicable.
10. ~~9-~~ Full urinalysis (protein content required, and optional parameters albumin and immunoglobulin G to be tested depending on study site capability) at Clinical Screening/baseline, and EOT; basic urinalysis (protein content only) on Days 43 and 85, and then every 6 weeks thereafter prior to administration of avelumab. If urinalysis (full or basic) is positive for protein, sediment will be evaluated.
11. ~~10-~~ In serum at Clinical Screening; in urine thereafter. Results of the most recent pregnancy test should be available prior to next administration of avelumab.

CCI

CCI

17. ~~46.~~ Premedication is mandatory approximately 30 to 60 minutes prior to the first 4 doses of avelumab. Premedication should be administered for subsequent avelumab doses based upon clinical judgment and presence/severity of prior infusion reactions. This regimen may be modified based on local treatment standards and guidelines as appropriate. However, the prophylactic use of systemic corticosteroids is not permitted.
18. ~~47.~~ All AEs will be documented at each study visit until the 30-day Safety Follow-up Visit. After this visit, only treatment-related nonserious AEs have to be documented until the 90-day Safety Follow-up Phone Call.
19. ~~48.~~ All SAEs will be documented at each study visit until the 90-day Safety Follow-up Phone Call. After this, all ongoing SAEs must be monitored and followed by the Investigator until stabilization or until the outcome is known, unless the subject is documented as lost to follow-up. Any SAE assessed as related to study drug must be reported whenever it occurs, irrespective of the time elapsed since the last administration of avelumab. At 90 days ( $\pm 5$  days) after the last dose of avelumab, subjects will be contacted by telephone to collect information on new or ongoing SAEs and treatment-related nonserious AEs.
20. ~~49.~~ Blood samples for PK and ADA will be collected as detailed in Table 1-4.
21. ~~20.~~ Subjects will be followed every 12 weeks ( $\pm 7$  days) for survival (including assessment of any further anticancer therapy).

**Table 12-4 Schedule of Assessments – Pharmacokinetic and Antidrug Antibody Sampling for Subjects Receiving Avelumab Once Every 2 Weeks**

Assessment	Treatment Phase													EOT Visit	Safety Follow-up	
	V1					V2		V3		V4		V7		Until Progression	Within 7 days after decision to discontinue IMP	30 days (± 5 days) after last IMP
	W1 D1		W1 D2	W1 D3	W2 D8	W3 D15		W5 D29		W7 D43		W13 D85				
	Prior to infusion	End of infusion				Prior to infusion	End of infusion									
PK sampling 	X	X	X	X	X	X	X	X	X	X	X	X	X	6-weekly up to W25 (D169), then 12-weekly	X	X
ADA sampling 	X					X		X		X		X		6-weekly up to W25 (D169), then 12 weekly to EOT		X

ADA: antidrug antibody; D: Day; EOT: End-of-Treatment; IMP: investigational medicinal product; PK: pharmacokinetics; V: Visit; W: Week.

1. For subjects receiving avelumab once every 2 weeks, PK serum samples will be collected at the following time points:

- Day 1: within 2 hours prior to and at the end of the 1-hour infusion, and at 0.5, 1, 2, 4, 6, and 12 hours after the end of the infusion.
- Day 2: 2 samples will be collected 24 and 36 hours after the end of the infusion.
- Day 3: a single sample will be collected 48 hours after the end of the infusion.
- Day 8: a single sample will be collected 168 hours after the end of the infusion.
- Days 15, 29, 43, 85, 127, and 169 (Week 25): samples will be collected within 2 hours prior to infusion (trough value) and immediately after the infusion is completed (peak value).
- Every 12 weeks beyond Week 25: a single sample will be collected within 2 hours prior to infusion (trough value).
- EOT Visit.
- 30-day Safety Follow-up Visit.

\*The time window for PK sampling timepoints are: + 10 minutes for the end of infusion sample collection on Day 1;  $\pm$  10 minutes for 0.5 and 1 hour after the end of infusion;  $\pm$  20 minutes for 2, 4, and 6 hours after the end of infusion;  $\pm$  2 hours for 12, 24, 36, 48, and 168 hours after the end of infusion. **The time window for PK sampling time points is applicable for all scheduled PK sample collection for all subjects.**

2. For subjects receiving avelumab once every 2 weeks, ADA serum samples will be collected at the following time points:
  - Day 1 (baseline): the baseline sample should be collected within 2 hours prior to the first administration of avelumab, ie, either during Clinical Screening or predose on Day 1.
  - Days 15, 29, 43, 85, 127 and 169: samples will be collected within 2 hours prior to infusion.
  - After Day 169, 1 sample (within 2 hours prior to infusion) every 12 weeks until the EOT Visit.
  - 30-day Safety Follow-up Visit.

AUC _{0-t}	Area under the concentration-time curve from time zero to time t
AUC _{0-tau}	Area under the concentration-time curve from time zero to tau, the respective dosing interval, i.e., one- or two-week
AUC _{0-tau/dose}	Dose-normalized AUC _{0-tau}
AUC _{extra%}	Percentage of area under the serum concentration-time curve from time zero to infinity (AUC _{0-∞}) obtained by extrapolation
BLQ	Below the limit of quantification
BMI	Body mass index
CCI	
C _{last}	Last quantifiable concentration
C _{max}	Maximum serum concentration
C _{max} /dose	Dose-normalized C _{max}
C _{min}	Minimum serum concentration
C _{trough}	Serum concentration observed immediately before next dosing
CR	Complete response
CRF	Case report form
CSR	Clinical Study Report
CTCAE	Common Terminology Criteria for Adverse Events
CV	Coefficient of variation
DCR	Disease control rate
DLT	Dose-limiting toxicity

CCI	
ECG	Electrocardiogram
ECOG	Eastern Cooperative Oncology Group
eCRF	Electronic case report form
EOT	End-of-Treatment
GeoCV%	Geometric coefficient of variation
GeoMean	Geometric mean
HIV	Human immunodeficiency virus
ICF	Informed Consent Form
ICH	International Council for Harmonization
IMP	Investigational medicinal product
irAE	Immune-related adverse event
IV	Intravenous(ly)
λ_z	Terminal elimination rate constant
Max	Maximum
Mean	Arithmetic mean
MedDRA	Medical Dictionary for Regulatory Activities
Min	Minimum
MSI	Microsatellite instability
MTD	Maximum tolerated dose
NCI	National Cancer Institute
NE	Not Evaluable

CCI

CCI

PD Progressive disease/disease progression

CCI

CCI

PK Pharmacokinetic(s)

CCI

PT	Preferred Term
RECIST	Response Evaluation Criteria in Solid Tumors
SAE	Serious adverse event
SCR	Screening Analysis Set
SDTM	Study Data Tabulation Model
SEM	Standard error of the mean
SOC	System Organ Class
IAP	Integrated Analysis Plan
IRR	Infusion Related Reactions
SD	Stable disease or standard deviation
SOD	Sum of longest diameter for non-nodal lesion and short axis for nodal lesion
$t_{1/2}$	Elimination half-life
T4	Thyroxine
TEAE	Treatment-emergent adverse event
TIL	Tumor infiltrating lymphocyte
t_{max}	Time to reach maximum serum concentration
TTR	Time to response
TSH	Thyroid-stimulating hormone
ULN	Upper limit of normal

3 Modification History

Unique Identifier for Version	Date of IAP Version	Author	Changes from the Previous Version
Draft 0.1	03NOV2017	PPD	Not Applicable
Draft 0.2	02MAR2018	PPD	Modified per sponsor's comments received on 22DEC2017 and 02FEB2018
Draft 0.3	11MAY2018	PPD	Modified per sponsor's comments received on 26MAR2018 and 10MAY2018.
Draft 0.4	29MAY2018	PPD	Modified per sponsor's comments received on 21MAY2018 and 24MAY2018.
Final 1.0	01JUN2018	PPD	Modified per sponsor's comments received on 25MAY2018 and 31MAY2018.
Final 2.0	13AUG2019	PPD	
 1. Add appendix of irAE and IRR 2. Add appendix of Toxicities for Laboratory Evaluations 3. Modify Section 12.2 Medications 4. Clarify ADA in secondary endpoint. 5. Add rule for incomplete date of prior/concomitant medication. 6. Modify definition of re-initiation

4 Purpose of the Integrated Analysis Plan

The purpose of this IAP is to document technical and detailed specifications for the final analysis of data collected for protocol MS100070-0035.

Results of the analyses described in this IAP will be included in the Clinical Study Report (CSR). Additionally, the planned analyses identified in this IAP will be included in regulatory submissions or future manuscripts. Any post-hoc, or unplanned analyses performed to provide results for inclusion in the CSR but not identified in this prospective IAP will be clearly identified in the CSR.

The IAP is based upon section 8 (Statistics) of the trial protocol and protocol amendments and is prepared in compliance with ICH E9.

5 Objectives and Endpoints

	Objective	Endpoint	IAP section
Primary Objective	
 • To evaluate the maximum tolerated dose (MTD) of avelumab (MSB0010718C) monotherapy in Chinese subjects. • To characterize the pharmacokinetics (PK) of avelumab in Chinese subjects. 	
Primary Endpoint
 
 • Occurrence of DLTs during the DLT observation period (first 21 days of treatment; excluding 10 mg/kg once weekly cohort). • PK profiles in Chinese subjects. 	
15
 
16.1
 
16.2

Secondary Objective	
 To determine the safety and tolerability of avelumab by assessing treatment-emergent adverse events (TEAEs) and treatment-related AEs for all dose groups according to the NCI-Common Terminology Criteria for Adverse Events (CTCAE) v4.03. To characterize immunogenicity of avelumab in Chinese subjects. 	Secondary Endpoint 
 Occurrence of TEAEs for all dose groups according to NCI-CTCAE v4.03. Occurrence of treatment-related AEs for all dose groups according to NCI-CTCAE v4.03. Serum titers of ADA against avelumab. 	14 15
----------------------------	---	---	----------

CCI

6 Overview of Planned Analyses

6.1 Interim Analysis

NA.

6.2 Primary Analysis

The primary analysis, including all endpoints analyses, for study data will be conducted at the time when all subjects complete PK sample collection (including all samples collected if the treatment discontinued earlier than Week 13). The data cut-off time point for primary analysis is set at Week 13 (Day 85) of the last subject.

The data from primary analysis will be summarized in the Clinical Study Report (CSR).

6.3 Final Analysis

The final analysis of study data will be conducted after End of Study, which is defined as the last patient complete 90-day safety follow-up phone call or last patient died, whichever comes first.

Additional data from primary analysis up to this cut-off date will be analyzed and presented as an addendum of CSR.

7 **Changes to the Planned Analyses in the Clinical Trial Protocol**

Biomarker related analysis are not planned in this IAP because biomarker testing will be done at a later time.

8 **Protocol Deviations and Analysis Sets**

8.1 **Definition of Protocol Deviations**

Important protocol deviations are protocol deviations that might significantly affect the completeness, accuracy, and/or reliability of the study data or that might significantly affect a subject's rights, safety, or well-being.

Important protocol deviations include:

- Subjects that receive study medication despite not satisfying the inclusion criteria or violating exclusion criteria;
- Subjects that develop withdrawal criteria whilst on the study but are not withdrawn;
- Subjects that receive the wrong treatment or an incorrect dose;
- Subjects that receive an excluded concomitant medication.

The following important deviations will be identified and confirmed prior to or at the Data Review Meeting:

- Deviations from the inclusion and exclusion criteria;
- Deviations post inclusion.

Important protocol deviations are specified in Appendix 18.1, and will be summarized in a table and presented in a data listing. All-important protocol deviations should be documented in SDTM datasets in which identified through sites monitoring, medical review or programming.

8.2 **Definition of Analysis Sets**

Screening Analysis Set (SCR): all subjects who signed the ICF(s).

DLT Analysis Set (DLT): all subjects with data used for implementing the dose-escalation schedule (excluding 6 subjects in 10 mg/kg once weekly cohort). These subjects should have received all avelumab administrations in the DLT observation period (first 21 days of treatment) or should have stopped treatment because of DLTs in the DLT observation period.

Safety Analysis Set (SAF): all subjects who have received at least 1 dose of avelumab. The Safety Analysis Set will be used for all analyses of safety and efficacy.

Efficacy Population: all subjects who have received at least 1 dose of avelumab and have measurable disease at baseline according to Investigator assessment.

PK Analysis Set: all subjects who receive at least one dose of avelumab, and provide at least one measurable post-dose concentration.

Immunogenicity Analysis Set: The immunogenicity analysis set will include all subjects who receive any dose of avelumab and who have at least one valid ADA result (including negative, positive-TNR).

9 General Specifications for Data Analyses

9.1 Data Handling After Cut-off Date

Data after cut-off date do not undergo the cleaning process. The only exception is the date of death on “DEATH” eCRF page and the date last known to be alive from the “FUPSTAT” eCRF page.

Generally, data others than the date of death and the date last known to be alive obtained after the cut-off will not be displayed in any listings or used for summary statistics, e.g., laboratory values of samples taken after cut-off date, AE with onset date after cutoff date etc. will not be included in any analysis or listing. However, AEs or medications with onset date before the cut-off will be displayed even if their end date is after the cut-off; either as ongoing or the end date will be reported (even though it is after the cut-off).

The data handling for cut-off date will be implemented at SDTM level.

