**Investigational Medicinal Product: dose/ mode of administration/ dosing schedule:**

Avelumab will be administered from a starting dose of 3 mg/kg up to a maximum dose of 20 mg/kg by IV infusion over 1 hour with the regimen of once every week or every 2 weeks until disease progression, significant clinical deterioration, unacceptable toxicity, or any criterion for withdrawal from the study or from avelumab occurs. For the every week regimen (6 subjects in the 10 mg/kg once weekly cohort), subjects will receive avelumab every week for 12 consecutive weeks and then starting at Week 13, once every 2 weeks thereafter.

To mitigate infusion-related reactions, a premedication regimen of 25 to 50 mg diphenhydramine and 500 to 650 mg acetaminophen (IV or oral equivalent) is mandatory approximately 30 to 60 minutes prior to the first 4 doses of avelumab. Premedication should be administered for subsequent avelumab doses based upon clinical judgment and presence/severity of prior infusion reactions. This regimen may be modified based on local treatment standards and guidelines as appropriate. However, the prophylactic use of systemic corticosteroids is not permitted.

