#### 5.1.1.1 Dose Escalation Design

The dose escalation of this study is based on a modified “3 + 3” cohort design. An initial cohort of 3 Chinese subjects with metastatic or locally advanced solid tumors will receive 3 mg/kg of

avelumab (IMP) once every 2 weeks. Each of these first 3 subjects will be observed for 21 days (DLT observation period). The SMC will review the safety data, including DLTs, and advise on further escalation to the next cohort (10 mg/kg of avelumab once every 2 weeks). As this study represents the introduction of avelumab into a new region, the 3 mg/kg dose has been selected as the starting dose, a minus 1 dose level to avelumab 10 mg/kg, as an extra precaution to further mitigate risks in Chinese subjects (Figure 5-3).

The 10 mg/kg once every 2 weeks cohort will enroll 6 Chinese subjects with metastatic or locally advanced solid tumors. Since more than 1400 subjects have been exposed to avelumab at a dose of 10 mg/kg once every 2 weeks and it has been well tolerated, it is unlikely that there are ethnic differences with respect to avelumab safety and PK; therefore staggered enrolment (3 + 3) will not be used for the 10 mg/kg once every 2 weeks cohort and all 6 slots will be opened at the same time for competitive recruitment.

After completion of 10 mg/kg once every 2 weeks cohort, the avelumab dose will be further escalated up to 20 mg/kg once every 2 weeks to characterize the safety and PK of avelumab at a higher dose level. A staggered “3 + 3” enrolment will be used for the 20 mg/kg avelumab cohort.

Once the safety of avelumab at 20 mg/kg once every 2 weeks have been established and can be regarded as safe (ie, no DLT observed in the first 3 subjects or less than 2 out of the 6 subjects experience a DLT), a new cohort of 10 mg/kg administered once weekly can be immediately initiated to assess safety of already established dose strength with a more frequent dose administration. Six (6) evaluable subjects are planned to be included in this cohort. The DLT assessment is not applicable for the 6 subjects in the 10 mg/kg once weekly cohort. Subjects in this cohort will receive avelumab at 10 mg/kg once weekly for the first 12 weeks. Starting from Week 13, dose frequency will be changed to once every 2 weeks. All 6 slots will be opened at the same time for competitive recruitment.

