15.2.2 Adverse Events Leading to Treatment Discontinuation

The frequency (number and percentage) of patients with each of the following will be presented for TEAEs leading to permanent discontinuation of avelumab, by treatment dose group:

- AEs leading to discontinuation of avelumab by SOC and PT
- Related AEs leading to discontinuation of avelumab by SOC and PT

15.2.3 The listing of all AEs leading to avelumab discontinuation will also be provided Deaths

The frequency (number and percentage) of patients who died during the trial period and who died within 30 days after last dose or 60 days after first dose of avelumab as well as the primary reason for death, will be tabulated based on information from the “DEATH” and “SUBJECT STATUS / SURVIVAL FOLLOW-UP” eCRF page.

The following summaries will be provided:

- All deaths
- Number of deaths within 30 days after last dose of study treatment
- Number of deaths within 60 days after first dose of study treatment
- Primary Reason of death
 - Progressive disease and/or disease related condition
 - Event unrelated to avelumab
 - Event related to avelumab
 - Event related to Physician's Choice
 - Unknown

In addition, date and cause of death will be provided in an individual subject data listing together with selected dosing information (study treatment received, date of first / last administration, number of infusions received for treatment, day relative to first infusion and day relative to most recent infusion) and will include the following information:

- AEs with fatal outcome (list preferred terms of AEs with outcome = Fatal, as well as AEs of Grade 5)
- Flag for death within 30 days of last trial drug treatment
- Flag for death within 60 days of first trial drug treatment

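### At the primary analysis the SAP keeps deaths after the cut-off but not later doses, so the count of deaths within 30 days of last dose can miss on-treatment deaths

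*SAP*

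**What the plan says.** SAP 6.2 fixes the primary cut-off: "The data cut-off time point for primary analysis is set at Week 13 (Day 85) of the last subject".

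SAP 9.1 governs later data. They are not cleaned, with this exemption: "The only exception is the date of death on “DEATH” eCRF page and the date last known to be alive". Its next paragraph repeats the same two exemptions and says that, generally, other data "obtained after the cut-off will not be displayed in any listings or used for summary statistics". Laboratory values and adverse events (AEs) are its examples. Records that span the cut-off are treated separately: "AEs or medications with onset date before the cut-off will be displayed even if their end date is after the cut-off". On execution it says: "The data handling for cut-off date will be implemented at SDTM level".

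SAP 15.2.3 (Deaths) tabulates all deaths, "Number of deaths within 30 days after last dose of study treatment", deaths within 60 days after first dose, and the primary reason for death. The listing adds a 30-day and a 60-day flag, the first and last administration dates, and the day relative to the most recent infusion. The section does not say which deaths are eligible at the primary analysis, or what last dose means for a subject still being treated.

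The Protocol synopsis has avelumab given "until disease progression, significant clinical deterioration, unacceptable toxicity, or any criterion for withdrawal from the study or from avelumab occurs". For the weekly cohort, Protocol 5.1.1.1 adds: "Starting from Week 13, dose frequency will be changed to once every 2 weeks". Protocol 7.1.5 allows survival follow-up to be refreshed at the time of the primary analysis.

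**The concern.** Time from last dose to death is only meaningful if both dates come from the same stretch of follow-up. Here the death date may come from after the cut-off, while the last dose cannot. For a subject who stopped avelumab before the cut-off this does no harm. For a subject who goes on being dosed, the retained last dose is earlier than the true one, so the computed interval can only be too long. The error therefore runs one way: deaths under treatment can drop out of the 30-day row, and none can be added to it.

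Death within 30 days of last dose is a basic safety figure. The study is small, and Protocol 3.3 says it will be part of the marketing submission in China, so one death moved out of that row is visible.

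**Working it through.** The documents give no figure for this, so there is nothing to reproduce. The check is date arithmetic.

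**Inputs**
- Cut-off taken as day 0 (SAP 6.2).
- Dosing every 14 days in all cohorts by then. The last subject is at Week 13, and the weekly cohort changes to two-weekly dosing at Week 13 (Protocol 5.1.1.1).
- Last retained dose g days before the cut-off, g = 0 to 13, if dosing is on schedule.
- Death L days after the cut-off, with dosing continuing on schedule until then.
- Planned size 21, up to 24 (Protocol synopsis).
- Time from cut-off to data snapshot: not given. Assumed 30 to 180 days.

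**Formulas**
- True interval from last dose to death = (g + L) mod 14, which is 0 to 13 days. Every such death belongs in the 30-day row.
- Interval after the cut = g + L.
- The death is missed when g + L > 30, that is, from L = 31 − g.

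**Results**
- Retained dose on the cut-off day (g = 0): missed from day 31. Retained dose 13 days before (g = 13): missed from day 18.
- Example with g = 7: doses at −7, +7, +21 and +35, death at +40. True interval 40 − 35 = 5 days; interval after the cut 7 + 40 = 47 days.
- Example with g = 0, such as the last subject dosed on Day 85: doses at 0, +14, +28 and +42, death at +45. True interval 3 days; interval after the cut 45 days.
- Weight of one death: 1/24 = 4.2% and 1/21 = 4.8%.

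**Share missed, given that an on-treatment death occurs between cut-off and snapshot.** With g and L uniform (an assumption) and a lag of S days, S at least 30, the share is [14(S − 30) + 91] / (14S), where 91 = 0 + 1 + … + 13.

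| S (days) | Missed / total | Share |
|---|---|---|
| 30 | 91 / 420 | 22% |
| 60 | 511 / 840 | 61% |
| 90 | 931 / 1,260 | 74% |
| 120 | 1,351 / 1,680 | 80% |
| 180 | 2,191 / 2,520 | 87% |

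**60-day count.** The last subject's first dose is 85 − 1 = 84 days before the cut-off, and no other subject's is later. Every death after the cut-off is thus more than 60 days after first dose, and that row and flag cannot be wrong.

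**With both dates from one window.** If both are carried to the snapshot, the interval is 0 to 13 days and the death counts. If both stop at the cut-off, the death is not assessed. Neither choice misclassifies it.

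**The case against.** The strongest reply is that SAP 9.1 never says dosing records are dropped. Its exemption sentence is about data cleaning, the display rule is qualified as general, and the examples are laboratory values and AEs. That is fair as far as it goes: removal of later infusions is inferred. The inference is strong, because the display rule names the same two exempt items and dosing is not one of them. The allowance for medications covers records begun before the cut-off, not new infusions.

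Second, the effect is temporary and traceable. SAP 6.3 reports the final analysis after End of Study, when dosing should be over, so the addendum should give the right count. The death listing shows the date of death beside the last administration, and SAP 10.1 reports how many subjects are still on treatment. A careful reader could spot the case. This stands and limits the weight of the point, but the primary report would still carry the wrong number.

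Third, the case may be rare. It needs dosing to continue after the cut-off and a death before the snapshot, whereas treatment normally stops at progression or clinical deterioration. This also stands. The row is descriptive, and dose escalation rests on 21-day dose-limiting toxicities.

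A reader might further infer that the death table should reconcile with the treatment-emergent AEs leading to death and that the cut-off breaks this. The documents do not support that. Those AEs must start by 30 days after last dose (SAP 15.2), while the death table also draws on survival follow-up, so the two differ by design. Nor does SAP 9.1 say outright that the reason for death is dropped. That too is inferred from the exemption naming only the dates.

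**Conclusion.** The point holds for three items at the primary analysis: the 30-day row, the 30-day flag, and the day relative to the most recent infusion. Followed as written, SAP 9.1 and 15.2.3 take the event and its anchor date from different windows, and the resulting error can only lengthen the interval. Each affected death shifts the 30-day percentage by 4.2 to 4.8 points. How many there will be is unknown and may be none, in which case nothing changes.

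This rests on later infusions being removed by the cut, on continued two-weekly dosing, and on deaths between cut-off and snapshot being captured. The shares of 22% to 87% also rest on the assumed lag and uniform timing. They are conditional on such a death and do not estimate how often one occurs.

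Three stronger readings go too far. SAP 15.2.3 has no row for deaths later than 30 days, so nothing is placed in a wrong category: the death is in the total and absent from the 30-day row. The 60-day count is unaffected. And nothing here requires later deaths to leave the total, since keeping them is a deliberate choice in SAP 9.1.

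**What to change.** State in SAP 9.1 and 15.2.3 that, for the 30-day row, the 30-day flag and the days-since-infusion column, death and last dose come from the same data window. Either option does this:

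- Limit those three items to deaths on or before the cut-off, with a footnote that the total also includes later deaths.
- Exempt the true last-dose date, and the primary reason for death, from the cut-off for subjects who die after it.

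Leave the total and the 60-day count as they are.

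The cost is one sentence and a small amount of programming. The first option assesses slightly fewer deaths in the 30-day row until the addendum. The second keeps every death assessable but needs a few extra dosing dates, and the reasons for death, to be cleaned.
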